7.5. Data Sources

7.5.1. Case report forms

The investigator will review source documents and complete an electronic CRF for each included patient. The completed original CRFs are the sole property of Pfizer and should not be made available in any form to the third parties, except for authorized representatives of Pfizer or appropriate regulatory authorities, without written permission from Pfizer.

The investigator has ultimate responsibility for the collection and reporting of all clinical, safety, and laboratory data entered on the CRFs, and ensuring that they are accurate, authentic/original, attributable, complete, consistent, legible, timely (contemporaneous), enduring, and available when required. The CRFs must be signed by the investigator or by an authorized staff member to attest that the data contained on the CRFs is true. Any corrections to entries made on the CRFs must be dated, initialed and explained (if necessary) and should not obscure the original entry.

In most cases, the source documents are the hospital's or the physician's patient chart. In these cases data collected on the CRFs must match the data in those charts.

7.5.2. Record retention

To enable evaluations and/or audits from regulatory authorities or Pfizer, the investigator agrees to keep records, including the original signed data privacy statement, identity of all participating patients (sufficient information to link records, e.g., CRFs and hospital records), copies of all CRFs, SAE forms, source documents, and detailed records of treatment disposition, and adequate documentation of relevant correspondence (e.g., letters, meeting minutes, telephone calls reports). The records should be retained by the investigator according to local regulations, or as specified in the Clinical Study Agreement, whichever is longer.

If the investigator becomes unable for any reason to continue to retain study records for the required period (e.g., retirement, relocation), Pfizer should be prospectively notified. The study records must be transferred to a designee acceptable to Pfizer, such as another investigator, another institution, or to an independent third party arranged by Pfizer. The investigator must obtain Pfizer's written permission before disposing of any records, even if retention requirements have been met.

7.6. Data Management

CRF data collected by the investigator will be entered into the clinical database. Verifications will be performed after comparison of the double data entry. All missing data or data to be checked will be reported on a query sheet for further verification at the study site. Any data modification will be recorded.

AEs will be coded using World Health Organization - Adverse Reaction Terminology. Medical history will be coded using Classification of Korea national statistical office. Concomitant drugs will be coded via www.kimsonline.co.kr provided by KIMS Co. Ltd.

Statistical analysis will be carried out with SAS software version 9.2 or a more recent version.

7.7. Data Analysis

The data collected in this study will be documented in a Statistical Analysis Plan, which will be maintained by the sponsor. This document may modify the plans outlined in the protocol; however, any major modifications of primary endpoint definitions or their analyses will be reflected in a protocol amendment.

No formal sample size calculations were performed for this study. Six hundred (600 patients) or more will be collected as per the requirement by MFDS. Safety summaries will be based on the safety analysis set defined as those patients who met inclusion / exclusion criteria and completed safety follow-up. Effectiveness summaries will be based on the effectiveness analysis set, defined as those patients who took at least 8 weeks of PRISTIQ® and completed effectiveness evaluation.

In addition, special subject groups -elderly group (more than or equal to 65 years old), hepatic disorder group, renal disorder group and pregnancy group- will be analyzed separately.

7.7.1. Safety analysis

- Count and frequency of occurrence of adverse event, serious adverse event, adverse drug reaction or unexpected adverse event by category.
- Count and frequency of occurrence of adverse events by subject baseline factor and by treatment factor to determine factors affecting the safety.
- If there is any particular pattern in abnormal findings (including clinical laboratory abnormalities) occurring during or after the treatment which were considered unrelated to PRISTIQ®, the count and frequency of the events will be tabulated and analyzed to determine the causal relationship to the relevant study drug.

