7.4.8. Clinical laboratory

If the physician performed laboratory test for diagnostics or monitoring in usual medical practice, check 'done' and record the results. If there are any clinically significant abnormality in laboratory test results during or after administration compared to one before administration, please check 'yes' and record the abnormality in "9. Safety evaluation" clause.

- Laboratory test item
- Normal range (unit)
- Date of laboratory test
- Test results (before / during / after)

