7.4.10.1. Definition of adverse events

An AE is any untoward medical occurrence in a patient administered a medicinal product. The event need not necessarily have a causal relationship with the product treatment or usage. Examples of adverse events include but are not limited to:

- Abnormal test findings (see below for circumstances in which an abnormal test finding constitutes an AE);

- Clinically significant symptoms and signs;
- Changes in physical examination findings;
- Hypersensitivity;
- Progression/worsening of underlying disease;
- Lack of efficacy;
- Drug abuse;
- Drug dependency.

Additionally, for medicinal products, they may include the signs or symptoms resulting from:

- Drug overdose;
- Drug withdrawal;
- Drug misuse;
- Off-label use;
- Drug interactions;
- Extravasation;
- Exposure during pregnancy;
- Exposure during breast feeding;
- Medication error;
- Occupational exposure.

Abnormal test findings

The criteria for determining whether an abnormal objective test finding should be reported as an adverse event are as follows:

- Test result is associated with accompanying symptoms, and/or
- Test result requires additional diagnostic testing or medical/surgical intervention, and/or

- Test result leads to a change in study dosing or discontinuation from the study, significant additional concomitant drug treatment, or other therapy, and/or
- Test result is considered to be an adverse event by the investigator or sponsor.

Merely repeating an abnormal test, in the absence of any of the above conditions, does not constitute an adverse event. Any abnormal test result that is determined to be an error does not require reporting as an adverse event.

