8.2.3 Other Analyses

Statistical analysis on blood pressure will be done on safety analysis set.

For Blood Pressure (SBP, DBP),

- Descriptive summary statistics (number of subjects (n), mean, standard deviation (SD), median, minimum and maximum) of blood pressure at before and after administration will be summarized.
- The change of after administration compared before administration for blood pressure will be analyzed using paired t-test.

In addition to the above summaries and analyses, the following Basic Results Tables will also be produced for the final study report.:

- Baseline Characteristics in safety analysis set
- Summary of Baseline Characteristics in safety analysis set
- All Adverse Events in safety analysis set
- Summary of Each SOC/PT of Adverse Events in safety analysis set
- Summary of Effectiveness Evaluation in effectiveness analysis set
- Subjects Flow Chart(the number of subjects who started the study, the number of subjects who completed the study)

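### The SAP specifies no analysis of the collected laboratory results and does not carry over the Protocol 7.7.1 pattern review; only abnormalities recorded as adverse events are counted

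*Protocol*

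**What the plan says.** Protocol 7.4.8 makes laboratory data conditional on routine care: "If the physician performed laboratory test for diagnostics or monitoring in usual medical practice, check 'done' and record the results". For each test the CRF takes the item, the normal range with unit, the date, and results at three stages, "Test results (before / during / after"). The investigator is also told, for any clinically significant "abnormality in laboratory test results during or after administration compared to one before administration, please check 'yes' and record the abnormality in" the safety evaluation part of the CRF.

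Protocol 7.4.10.1 sets out when an abnormal test counts as an AE and adds a limit: "Merely repeating an abnormal test, in the absence of any of the above conditions, does not constitute an adverse event".

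The third item of Protocol 7.7.1 opens "If there is any particular pattern in abnormal findings (including clinical laboratory abnormalities) occurring during or after the treatment" and continues "which were considered unrelated to PRISTIQ®, the count and frequency of the events will be tabulated and analyzed to determine the causal relationship" to the study drug.

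In the SAP, the only safety endpoint (6.1) is the occurrence of an AE. Section 8.2.1.4 presents AEs by preferred term and repeats the table by causality and by other causality. Section 8.2.3 turns to data other than AEs: "Statistical analysis on blood pressure will be done on safety analysis set", followed by the Basic Results Tables. None of these is a laboratory output.

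**The concern.** The protocol names laboratory abnormalities in its safety analysis and collects what is needed to look at them, including a reference range for every test. The SAP is silent on them. The contrast with blood pressure is plain. Protocol 7.4.7 collects blood pressure on the same routine-practice terms, also before, during and after, and also sends clinically significant changes to the safety evaluation. Blood pressure has its own SAP analysis, added in SAP version 2.0. Laboratory data have none, and no reason is given.

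At stake is a signal that only pooling can show. Results that move outside the normal range in several patients at different centres, none recorded as an AE, would appear in no output. Those that are recorded as AEs and judged unrelated would be counted, but the SAP has no step at which anyone looks across them, as Protocol 7.7.1 intends.

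**Working it through.** No figure in the plan depends on this point, so the check is to follow a laboratory result through the two documents.

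1. Collection (Protocol 7.4.8). A result enters the CRF if the physician ordered the test in usual practice. No test is mandated, so the number of subjects tested is unknown.

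2. Route to AE status (Protocol 7.4.8 and 7.4.10.1). A result becomes an AE if the investigator finds a clinically significant abnormality compared with before treatment. It also becomes one if it comes with symptoms, leads to further testing or intervention, changes dosing or other therapy, or is considered an AE by the investigator or the sponsor. Other abnormal results stay in the laboratory part of the CRF.

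3. Results that become AEs (SAP 8.2.1.4). They are counted by preferred term, and again by causality. 'Unlikely' is the only category outside the adverse drug reaction definition, and such events remain in the AE tables. A laboratory AE judged unrelated is therefore counted.

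4. Results that do not become AEs (SAP 6.1, 8.2.1 to 8.2.3, 9.1). No summary, shift table, change from baseline or listing uses them.

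5. The review itself (Protocol 7.7.1). It is triggered by a particular pattern. Neither document defines one, and the SAP names no output to be inspected for one and no step that re-examines events coded 'Unlikely'. The table in step 3 counts investigators' judgments without reviewing them.

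6. Denominator. SAP 8.1.2 sets the denominator for categorical summaries as the analysis set. For a finding that can be seen only in tested subjects, the share shown is the share among those tested multiplied by m/N, where m is the number tested and N the analysis set. The enrolment target of 600 stands in for N; the safety analysis set may differ. The values of m and the count of 5 are assumptions, because the documents give neither:

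| Assumed m | 5/m | 5/600 |
|---|---|---|
| 100 | 5.0% | 0.8% |
| 150 | 3.3% | 0.8% |
| 300 | 1.7% | 0.8% |

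The understatement is by a factor N/m, here 6, 4 and 2.

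7. Precision, for illustration only. With no normal-to-abnormal shift among n subjects with both results, the exact two-sided 95% upper limit is 1 − 0.025^(1/n). This is 3.6% for an assumed n = 100 and 1.2% for n = 300. The true n is unknown, and such a limit would describe only those tested.

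**The case against.** The strongest reply is that Protocol 7.7.1 is already served. It concerns findings considered unrelated, and this protocol records causality only for AEs (7.4.10.3). A laboratory value never entered as an AE has no causality field. On that reading the material for 7.7.1 is the AEs coded 'Unlikely', and SAP 8.2.1.4 gives their counts and percentages by term. Further, 7.7.1 is conditional and promises no standing laboratory table. Testing is selective, with unstandardised timing and ranges, so shift rates could suggest a precision the data lack.

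Much of this stands, and it rules out some stronger readings:

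- A reader might infer that the 7.7.1 check is never made, or that it cannot be made from AE entries. The documents do not support either. The AE-by-causality table supplies counts for laboratory AEs judged unrelated, and 7.4.10.1 gives several routes to AE status, including one through the sponsor.
- A reader might infer that a protocol analysis was dropped in breach of the amendment rule. Protocol 7.7 says of the SAP, "This document may modify the plans outlined in the protocol", and asks for an amendment only for major modifications of primary endpoint definitions or their analyses. This item is neither.

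The reply does not remove the gap. Even on the narrow reading, the SAP does not link the causality table to the 7.7.1 review. A conditional analysis still needs a step at which the condition is examined. Selective testing is a reason to label the output descriptive and to use the right denominator; it does not explain silence about collected safety data.

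**Conclusion.** The point holds in a limited form. The SAP specifies no analysis of laboratory values and does not carry over the Protocol 7.7.1 review. Abnormalities recorded as AEs are counted in SAP 8.2.1.4, over the analysis set rather than the subjects tested. All other laboratory results are unused.

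The size cannot be stated, because the documents do not give the number tested; the percentages above are illustrations on assumed counts. No sample size, primary result or stated figure is affected. The conclusion rests on reading every SAP section and finding no laboratory output, and on taking the general denominator rule of SAP 8.1.2 to apply to the AE tables. It is worth correcting because finding safety problems after marketing is the purpose of the study and the data are already collected.

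**What to change.** Add to SAP 8.2.3:

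- For each laboratory test with a before and a during/after result, a descriptive shift table (within or outside the recorded normal range), with the subjects having both results as denominator. State which result is used when a subject has several.
- A listing of normal-to-abnormal shifts that were not recorded as an AE or were coded 'Unlikely'.
- A statement that testing was at the physician's discretion, so the results are descriptive. Any exact confidence interval should be two-sided and described as applying only to those tested.

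Add to SAP 8.2.1.4 a sentence naming the 'Unlikely' rows of the causality table as the input to the Protocol 7.7.1 pattern review.

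The cost is a SAP revision, one table layout and one listing, all from collected data. Protocol 7.7 does not require an amendment for this. The downside is that selective, unstandardised testing limits interpretation, and some crossing of a normal range is expected without any drug effect. If the sponsor prefers not to add the outputs, the SAP should at least say that laboratory values will not be analysed and that the causality table serves the 7.7.1 item.

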7.7.2. Effectiveness analysis

Effectiveness endpoints include following variables: CGI-I scale and final effectiveness evaluation result at the date of effectiveness evaluation. Descriptive statistics (cell counts and percents) will be used to summarize this variable within the effectiveness analysis set population; the CGI-I scale and final effectiveness evaluation will also be summarized within subgroups of the effectiveness analysis set formed by demographic and other baseline factors such as sex, age and diagnosis date of MDD, etc. Comparisons across subgroups may be conducted using chi-squared tests at the 0.05 level of significance.

7.7.3. Statistical consideration

The significance of the difference between sub-categories with regard to safety and effectiveness will be statistically analyzed using χ^2 test ($p \leq 0.05$), etc. The frequency of occurrence of each adverse event will be presented with its 95% confidence interval.

To determine factors affecting the safety, the count and frequency of occurrence of all adverse events will be tabulated by type of the event and subject's baseline factor (gender, age, presence of concurrent disease, etc.), and factors considered potentially affecting the safety will be analyzed using categorical data analysis method (Chi-square test, Fisher's Exact test), etc. Serious adverse events, adverse drug reaction and unexpected adverse events, etc. will be also tabulated and summarized.

7.8. Quality Control

Quality assurance audits will be performed at study centers by the Pfizer's own independent quality assurance group or by clinical research organization. These audits will be conducted according to Pfizer's procedures and the guidelines for Good Pharmacoepidemiology Practices (GPP) (see [Section 8.4](#)).

7.9. Limitations of the Research Methods

This is a non-interventional PMS study conducted in the Republic of Korea to satisfy the requirements of MFDS. The protocol is determined by regulation of MFDS and not the specific disease and drug characteristics. The observational, non-controlled, and non-randomized design of this study has intrinsic limitations.

8. PROTECTION OF HUMAN SUBJECTS

8.1. Patient Information and Consent

All parties will ensure protection of patient personal data and will not include patient names on any sponsor forms, reports, publications, or in any other disclosures, except where required by laws. In case of data transfer, Pfizer will maintain high standards of confidentiality and protection of patient personal data.

The data privacy statement must be in compliance with local regulatory requirements and legal requirements.

The data privacy statement used in this study, and any changes made during the course of the study, must be prospectively approved by both the Institutional Review Board (IRB)/Independent Ethics Committee (IEC) and Pfizer before use.

The investigator must ensure that each study patient, or his/her legally acceptable representative, is fully informed about the nature and objectives of the study and possible risks associated with participation. The investigator, or a person designated by the investigator, will obtain written data privacy statement from each patient or the patient's

legally acceptable representative before any study-specific activity is performed. The investigator will retain the original of each patient's signed data privacy statement.

8.2. Patient Withdrawal

Patients may withdraw from the study at any time at their own or their legally acceptable representative's request, or they may be withdrawn at any time at the discretion of the investigator or sponsor for safety, behavioral, or administrative reasons. In any circumstance, every effort should be made to document subject outcome, if possible. The investigator should inquire about the reason for withdrawal and follow-up with the subject regarding any unresolved adverse events.

If the patient withdraws from the study, and also withdraws consent for disclosure of future information, no further evaluations should be performed, and no additional data should be collected. The sponsor may retain and continue to use any data collected before such withdrawal of consent.

8.3. Institutional Review Board (IRB)/Independent Ethics Committee (IEC)

The study protocol will be submitted to MFDS prior to the study. The ethical consideration on this study will be evaluated by IRB/IEC in each clinical site prior to the study if the site has an approval process for this PMS study according to the local standard operation procedure of the site.

It is the responsibility of the investigator to have prospective approval of the study protocol, protocol amendments, and other relevant documents, if applicable, from the IRB/IEC. All correspondence with the IRB/IEC should be retained in the Investigator File. Copies of IRB/IEC approvals should be forwarded to Pfizer or its designee.

8.4. Ethical Conduct of the Study

The study will be conducted in accordance with legal and regulatory requirements, as well as with scientific purpose, value and rigor and follow generally accepted research practices described in Guidelines for GPP issued by the International Society for Pharmacoepidemiology (ISPE), Good Epidemiological Practice (GEP) guidelines issued by the International Epidemiological Association (IEA), Pharmaceutical Research and Manufacturers Association (PhRMA) guidelines, and Korea PMS regulations and/or guidelines.

9. MANAGEMENT AND REPORTING OF ADVERSE EVENTS

9.1. Requirements

The table below summarizes the requirements for recording safety events on the CRF and for reporting safety events on the non-interventional study (NIS) adverse event monitoring (AEM) Report Form to Pfizer Safety. These requirements are delineated for three types of events: (1) serious adverse events (SAEs); (2) non-serious AEs (as applicable); and (3)

scenarios involving drug exposure, including exposure during pregnancy, exposure during breast feeding, medication error, overdose, misuse, extravasation, and occupational exposure. These events are defined in the section “Definitions of safety events”.

Safety event	Recorded on the CRF	Reported on the NIS AEM Report Form to Pfizer Safety within 24 hours of awareness
SAE	All	All
Non-serious AE	All	None
Scenarios involving exposure to a drug under study, including exposure during pregnancy, exposure during breast feeding, medication error, overdose, misuse, extravasation; lack of efficacy; and occupational exposure	All (regardless of whether associated with an AE), except occupational exposure	All (regardless of whether associated with an AE)

For each AE, the investigator must pursue and obtain information adequate both to determine the outcome of the adverse event and to assess whether it meets the criteria for classification as a SAE (see section "Serious Adverse Events" below)

Safety events listed in the table above must be reported to Pfizer within 24 hours of awareness of the event by the investigator **regardless of whether the event is determined by the investigator to be related to a drug under study**. In particular, if the SAE is fatal or life-threatening, notification to Pfizer must be made immediately, irrespective of the extent of available event information. This timeframe also applies to additional new (follow-up) information on previously forwarded safety event reports. In the rare situation that the investigator does not become immediately aware of the occurrence of a safety event, the investigator must report the event within 24 hours after learning of it and document the time of his/her first awareness of the events.

For safety events that are considered serious or that are identified in the far right column of the table above that are reportable to Pfizer within 24 hours of awareness, the investigator is obligated to pursue and to provide any additional information to Pfizer in accordance with this 24-hour timeframe. In addition, an investigator may be requested by Pfizer to obtain specific follow-up information in an expedited fashion. This information is more detailed than that recorded on the CRF. In general, this will include a description of the adverse event in sufficient detail to allow for a complete medical assessment of the case and independent determination of possible causality. Any information relevant to the event, such as concomitant medications and illnesses must be provided. In the case of a patient death, a summary of available autopsy findings must be submitted as soon as possible to Pfizer or its designated representative.

